23. AE Assessment: AEs should be documented and recorded at each visit using NCI CTCAE version 4.03. Patients must be followed for AEs for 28 days after the last treatment administration or until all drug related toxicities have resolved, whichever is later; or earlier than 28 days should the patient commence another anticancer therapy in the meantime. For SAEs, the active reporting period to Pfizer or its designated representative begins from the time that the patient provides informed consent, which is obtained prior to the patient’s participation in the study, ie, prior to undergoing any study related procedure and/or receiving investigational product, through and including 60 calendar days after the last administration of the investigational product. SAEs experienced by a patient after the active reporting period has ended should be reported to

the Sponsor if the investigator becomes aware of them; at a minimum, all SAEs that the investigator believes have at least a reasonable possibility of being related to study drug are to be reported to the Sponsor.

24. Concomitant Medications: All concomitant medications including supportive care drugs (eg, Anti emetic treatment and prophylaxis), and the drugs used to treat AEs or chronic diseases should be recorded in the CRF.

CCI

30. Central Histopathology Review of FL Diagnosis (Portion B only): Slides from the archival (tissue collected within the last 6 months) OR a baseline (tissue collected *de novo* during the screening period prior to the first dose of PF-05082566) tumor biopsy must be sent to a central pathology laboratory for independent review. Confirmation of the FL diagnosis is not required for patient enrollment. See the study manual for more details.

CCI

32. Bone marrow (BM) biopsy or aspirate: Required for patients with potential CR by radiological assessments to determine the response category.

Table 6. Schedule of Activities: Portion A (PF-05082566 Alone: Dose Expansion Cohorts): Pharmacokinetic assessments

Assessments [(±) 2 days for cycles >1]	Cycle 1			Cycle 2 and 3	Cycle 4			Cycle ≥5	End of Treatment	
	Day 1	Day 7	Day 14	Day 1	Day 1	Day 7	Day 14	Day 1		
Blood for PF-05082566 PK ¹	X	X	X	X	X	X	X	X (every 4 cycles)	X	
Blood for Immunogenicity (ADA) testing ²	X			X	X			X (every 4 cycles)	X	

1. Blood for PF-05082566 Pharmacokinetics: Blood samples will be collected for at least 5 patients in each dose expansion cohort with the following schedule: during Cycle 1 on (a) Day 1 at pre-dose, end of infusion, and at 2, 6, and 24 hrs post start of infusion; (b) 1 sample on Days 7 and 14, respectively. During Cycle 2 and Cycle 3 on (c) Day 1 at pre-dose, and end of infusion. During Cycle 4 on (d) Day 1 at pre-dose, end of infusion, and at 2, 6, and 24 hrs post start of infusion; (e) 1 sample on Days 7 and 14, respectively. After Cycle 4, PK samples will be collected on Day 1 at pre dose every 4 cycles. For the remaining patients, PK samples will be collected on Day 1 of Cycles 1 to 4 at pre-dose and end of infusion. After Cycle 4, PK samples will be collected on Day 1 at pre-dose every 4 cycles. A PK sample should be collected at the End of Treatment assessment. In Japan, patients will be hospitalized for PK sampling for at least the first two days of the first cycle of dosing of PF-05082566.
2. Blood for Immunogenicity (ADA) testing: Blood for immunogenicity testing will be collected at a) Day 1 at pre-dose from Cycle 1 to Cycle 4; b) after Cycle 4, ADA samples will be collected on Day 1 at pre-dose every 4 cycles. Immunogenicity samples should be collected at the End of Treatment assessment day.

Table 7. Schedule of Activities: Portion B (PF-05082566 + Rituximab: Dose Expansion): Pharmacokinetic Assessments

Assessments (Cycle Day relative to PF-05082566 dosing)	Cycle 1					Cycle 2 and 3	Cycle 4			Cycle ≥5		End of Treatment
	Day (-7)	Day (0)	Day 1	Day 7	Day 14	Day 1	Day 1	Day 7	Day 14	Day 1		
Blood for PF-05082566 PK ¹			X	X	X	X	X	X	X		X (every 4 cycles)	X
Blood for Rituximab PK ²	X	X	X	X	X	X (C2 only)						X
Blood for PF-05082566 Immunogeni city (ADA) testing ³			X			X	X				X (every 4 cycles)	X
Blood for Rituximab immunogenicity (ADA) testing ⁴	X	X		X	X	X (C2 only)						X

- Blood for PF-05082566 Pharmacokinetics: Blood samples will be collected for at least 5 patients in each dose expansion cohort (dosed with PF-05082566 at 1.2 mg/kg OR 0.24 mg/kg) with the following schedule: during Cycle 1 on (a) Day 1 at pre-dose, end of infusion, and at 2, 6 and 24 hr post start of infusion; (b) 1 sample on Days 7 and 14, respectively. During Cycle 2 and Cycle 3 on (c) Day 1 at pre-dose, end of infusion. During Cycle 4 on (d) Day 1 at pre-dose, end of infusion, and at 2, 6 and 24 hr post start of infusion; (e) 1 sample on Days 7 and 14, respectively. After Cycle 4, PK samples will be collected on Day 1 at pre-dose every four cycles. For the remaining patients, PK samples will be collected on Day 1 of Cycles 1 to 4 at pre-dose and end of infusion. After Cycle 4, PK samples will be collected on Day 1 at pre-dose every 4 cycles. A PK sample should be collected at the End of Treatment assessment.
- Blood for Rituximab Pharmacokinetics (NOTE: All days are numbered relative to PF-05082566 dosing): Blood samples will be collected for at least 5 patients enrolled in the dose expansion cohort dosed with PF-05082566 at 1.2 mg/kg on (a) Day -7) and Day (0) at pre- dose and end of infusion of rituximab (b) on Cycle 1 Day 1 at 2 and 24 post start of infusion of PF-05082566; (c) on Cycle 1 Day 7 and Day 14 at pre-dose and end of infusion of rituximab; (f) 1 sample on Cycle 2 Day 1 before the dose of PF-05082566; PK samples should be collected at the End of treatment/Withdrawal assessment day. For the remaining patients, PK samples for rituximab will NOT be collected. Note that whenever rituximab PK samples are collected on days when PF-05082566 PK samples are collected, they should be time matched to avoid multiple sticks.
- Blood for PF-05082566 Immunogenicity (ADA) testing: Blood for immunogenicity testing will be collected at a) Day 1 at pre-dose from Cycle 1 to Cycle 4 b) after Cycle 4, ADA samples will be collected on Day 1 at pre-dose every four cycles (Cycle 8, Cycle 12, etc.). Immunogenicity samples should be collected at the End of Treatment assessment day.
- Blood for Rituximab Immunogenicity (ADA) testing (NOTE: All days are numbered relative to PF-05082566 dosing): Blood for immunogenicity testing will be collected at a) Cycle 1 On Day (-7), Day 0, Day 7 and Day 14 prior to the dosing of rituximab; (b) On Cycle 2 Day 1 prior to the dosing of PF-05082566; (d) end of treatment.

Table 8 Safety Laboratory Tests

SAFETY LABORATORY REQUIREMENTS	
- May be performed up to 48 hours prior to scheduled cycle Day 1 visits to facilitate availability of results to the investigator at the time of the clinic visit.	
Assessments	
Hematology Panel:	Chemistry Panel:
Absolute Neutrophil Count	Sodium
Hemoglobin	Potassium
	Calcium
Platelet Count	Creatinine
WBC with differential (5-part if available)	Albumin
	Alanine aminotransferase (ALT)
	Aspartate aminotransferase (AST)
	Glucose
	Phosphorus
	Magnesium
	Bilirubin: total
	Blood urea nitrogen (BUN)
	Alkaline phosphatase
	Lactate dehydrogenase (LDH)
	Total protein
	Uric acid (or urate)
Coagulation Panel: international normalized ratio (INR) or prothrombin time (PT), Partial thromboplastin time (PTT)	Hepatitis Screening: hepatitis B surface antigen and core antibody; anti-hepatitis C antibody.

Table 8 Safety Laboratory Tests

SAFETY LABORATORY REQUIREMENTS	
- May be performed up to 48 hours prior to scheduled cycle Day 1 visits to facilitate availability of results to the investigator at the time of the clinic visit.	
Assessments	
Urinalysis: measurement of pH, specific gravity, protein/albumin, glucose, blood/hemoglobin, ketones/acetone, Urine dipstick for urine protein: if positive collect 24-hr and microscopic (Reflex Testing), Urine dipstick for urine blood: if positive collect a microscopic (Reflex Testing). No need to repeat on C1D1 if baseline assessment performed within 7 days prior to that date. Pregnancy Test (serum or urine): Conducted for women of childbearing potential only.	Endocrine Function Assessments: baseline assessments including but not limited to: TSH, Free T4. In the presence of clinical suspicion of hypopituitarism or hypoadrenalism, laboratory testing should include one or more of the following: TSH, ACTH, and cortisol levels before and 30-60 minutes after corticotropin stimulation.

TABLE OF CONTENTS

LIST OF TABLES	53
LIST OF FIGURES	53
APPENDICES	54
1. INTRODUCTION	55
1.1. Mechanism of Action/Indication.....	55
1.2. Background and Rationale	55
1.2.1. Scientific Rationale: Target Biology and Mechanism of Action.....	55
1.2.2. Pre-Clinical Development of PF-05082566	56
1.2.2.1. In Vitro Data.....	56
1.2.2.2. In Vivo Data: Functional Activity of PF-05082566.....	57
1.2.2.3. Anti-Tumor Activity of PF-05082566	58
1.2.2.4. Combination Studies	58
CCI	
CCI	
CCI	
CCI	
1.4. Study Rationale	62
1.5. Summary of Benefit/Risk Assessment.....	63
2. STUDY OBJECTIVES AND ENDPOINTS.....	64
2.1. Objectives.....	64

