Baseline Signs and Symptoms ⁹	X								
Vital Signs (BP, pulse, body temperature for Portion B) ¹⁰	X	X	X	X	X	X	X	X	
Neurological Examination (Portion B) ²⁹	As clinically indicated								
Central histopathology review of FL diagnosis (Portion B) ³⁰	X								
Safety Labs /Measurements									
12-Lead ECG ¹¹	X	X		X			X (C2, C3, C4)	X	
Hematology and Blood Chemistry ¹²	X	X	X	X	X	X	X	X	
Coagulation ¹³	X	X	X	X	X	X	X	X	
Urinalysis ¹⁴	X			X				X	
Pregnancy test ¹⁴	X			X			X	X	
Hepatitis B and C testing [hepatitis B surface antigen and core antibody; anti-hepatitis C antibody]	X								
Endocrine function assessment ¹⁶	X						X	X	
LVEF assessment ¹⁷	X			As clinically indicated					
Registration and Treatment									
Registration ¹⁸		X		X					
Administration of PF-05082566 ¹⁹				X			X		

2. End of Treatment: To be performed approximately 28 days after the last dose of study treatment. Obtain these assessments if not completed during the previous week (during the previous 6 weeks for tumor assessments).
3. Follow-up period: Patients should be evaluated for adverse events up to 60 days after last dose of study treatment. Patients continuing to experience toxicity at this point following discontinuation of treatment will continue to be followed at least every 4 weeks until resolution or determination, in the clinical judgment of the Investigator, that no further improvement is expected. Patients whose disease has not progressed at the end of treatment will enter into disease follow-up. During this follow-up period, patients will have disease assessments performed every 16 weeks (± 1 week). Once patients have exhibited disease progression, they will enter into survival follow-up for assessment of survival only. Any new anti-cancer therapy will be reported on the CRF. Survival follow-up will be conducted every 12 weeks (± 4 weeks) for survival status and subsequent anti-cancer treatment, up to 2 years from the first dose of study treatment for the last treated patient (for the non-randomized cohorts) or from the randomization date for the last randomized patient (for the randomized cohorts). Telephone calls are acceptable.

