11. Triplicate 12 Lead ECG: At each time point, 3 consecutive 12 lead ECGs will be performed approximately 2 minutes apart to determine mean QTc. When coinciding with blood sample draws for PK, ECG assessment should be performed prior to blood sample collection, such that the blood sample is collected at the nominal time. ECGs will be collected as follows: a) at Screening; b) On Day -7, prior to the dose of Rituximab and at end of infusion (Portion B only); c) On Cycle 1 Day 1 (C1D1), prior to the dose of PF-05082566 and 1.5 hours post start of infusion; d) On Cycle 2-4 Day 1 at 1.5 hours post start of infusion; and e) at End of Treatment. Additional triplicate ECGs may be performed as clinically indicated. If the QTc interval is prolonged (>500 msec by any correction method), then the ECGs should be re-evaluated by a qualified person at the center for confirmation. A subset of approximately 30 FL patients enrolled at selected sites in the FL-3 expansion cohort of Portion B will be assessed using an ECG machine provided by central vendor to allow central review of ECG.
12. Hematology and Chemistry: No need to repeat on C1D1 for Portion A or Cycle 1 Day -7 [C1D(-7)] for Portion B if the screening assessment is performed within 7 days prior to that date. To be performed weekly only for portion B patients during Cycle 1, and on Day 1 for all subsequent cycles. See [Table 8](#) for Laboratory Tests list.
13. Coagulation: No need to repeat on C1D1 (Portion A) or C1D(-7) (Portion B) if the screening assessment is performed within 7 days prior to that date. To be performed weekly only for portion B patients during Cycle 1, and on Day 1 of all subsequent cycles. See [Table 8](#) for Laboratory Tests list.

14. Urinalysis: Dipstick is acceptable. Microscopic analyses if dipstick abnormal. No need to repeat on C1D1 (Portion A) if the screening assessment is performed within 7 days prior to that date. To be performed at screening, Cycle 1 Day 1, and at the end of treatment. See [Table 8](#) for Laboratory Tests list.

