15. Serum/Urine Pregnancy Test: For female patients of childbearing potential, who do not fit for the definition of “female patients of nonchildbearing potential” in inclusion criterion 11, a serum or urine pregnancy test, with sensitivity of at least 25 mIU/mL, will be performed on 2 occasions prior to starting administration of study treatment: once at the start of screening and once at the baseline visit, immediately before administration of the first dose of study treatment. Pregnancy tests will also be routinely repeated at every cycle during the active treatment period, at the end of study therapy and additionally whenever one menstrual cycle is missed or when potential pregnancy is otherwise suspected. Additional pregnancy tests may also be undertaken if requested by institutional review board/ethics committee (IRB/ECs) or if required by local regulations.
16. Endocrine function assessment: thyroid function testing should be performed at screening, on Cycle 3 Day 1, every 12 week thereafter, and at the end of treatment; ACTH and cortisol levels should be assessed in cases of suspected hypoadrenalism or hypopituitarism. See [Table 8](#) for Laboratory Tests list.
17. LVEF assessment: measurement of ejection fraction by echocardiogram (ECHO), multigated acquisition (MUGA) scan, or an equivalent methodology.
18. Registration: In the randomized cohorts of Portion A for patients with advanced melanoma, patient enrollment and assignment of PF-05082566 dose level is managed through the use of an interactive response technology (IRT) system. In the non-randomized cohorts of Portion A and Portion B patient number and dose level allocation is operated by Pfizer.
19. PF-05082566 administration: PF-05082566 will be administered once every 4 weeks as a 1 hour (-5/+15 min) IV infusion (each cycle =28 days). For the randomized cohorts in Portion A patients will be randomized 2:1:1 to the 0.6 mg/kg, 1.2 mg/kg and 0.24 mg/kg dose levels of PF-05082566, respectively. Patients enrolled in the non-randomized cohorts of Portion A and Portion B will receive either the 1.2 mg/kg or 0.24 mg/kg dose level of PF-05082566.
20. Rituximab administration (Portion B only): rituximab (375 mg/m²) will be administered as an IV infusion once weekly for 4 doses during Cycle 1 starting on Cycle 1 Day -7. Refer to [Section 5.4](#) of the protocol on administration and management of infusion related AEs and to the rituximab package insert.

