4.2. Exclusion Criteria

Patients presenting with any of the following will not be included in the study:

1. Patients with known symptomatic brain metastases requiring steroids. Patients with previously diagnosed brain metastases are eligible if they have completed their treatment and have recovered from the acute effects of radiation therapy or surgery

- prior to enrollment (Portion B) or randomization (Portion A), have discontinued corticosteroid treatment for these metastases for at least 4 weeks and are neurologically stable.
2. Prior allogeneic hematopoietic stem cell transplant.
 3. Chemotherapy, growth factors, or investigational agents within 28 days before the first dose of study treatment (for the purposes of this protocol, study treatment includes rituximab in Portion B). Immunosuppressive regimens involving systemic corticosteroids within 14 days before the first dose of study treatment.
 4. Therapeutic or experimental monoclonal antibodies in last 28 days prior to enrollment (Portion B) or randomization (Portion A).
 5. Prior therapy with a compound of the same mechanism of action.
 6. Vaccination within 4 weeks prior to enrollment (Portion B) or randomization (Portion A) except for administration of inactivated vaccines (for example, inactivated influenza vaccines).
 7. Major surgery within 28 days prior to enrollment (Portion B) or randomization (Portion A).
 8. Radiation therapy within 14 days prior to enrollment (Portion B) or randomization (Portion A).
 9. Autoimmune disorders (eg, Crohn's Disease, rheumatoid arthritis, scleroderma, systemic lupus erythematosus) and other diseases that compromise or impair the immune system.
 10. Active and clinically significant bacterial, fungal or viral infection including tuberculosis, hepatitis B (HBV), hepatitis C (HCV), known human immunodeficiency virus (HIV) or acquired immunodeficiency syndrome (AIDS)-related illness (HIV testing is not required).

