PF-05082566 will be administered at 2 planned dose escalation levels (5.0 mg/kg and 10 mg/kg) by IV infusion of 1 hour (-5/+15 min) every 4 weeks. Each patient will initially receive the first dose on Cycle 1 Day 1 with a 28-day observation period. Cycle 2 Day 1 will start on Day 29. After completion of Cycle 2, patients will be asked to sign an additional consent document for confirmation of the patient's willingness to continue participation in this study before starting Cycle 3. Lower dose levels, as described above for Portion A, may be explored at any time during the study if this is clinically and scientifically warranted based on the emerging safety data in Japanese patients. Study centers will receive a notification if additional dose levels are explored.

Portion B:

PF-05082566 will be administered by IV infusion of 1 hour (-5/+15 min) every four weeks at dose levels as shown for Portion A, with the exception that the Portion B dose escalation starts at 0.03 mg/kg.

In the expansion cohort, patients enrolled in Portion B will receive a dose of PF-05082566 at 0.24 mg/kg or 1.2 mg/kg in combination with 375 mg/m² rituximab. If a PF-05082566 dose reduction is required due to the PF-05082566-related toxicity, this may be allowed as an alternative to discontinuation of treatment. No dose reduction is allowed for patients treated at the 0.24 mg/kg dose level. See [Section 5.4.4](#) for details.

Rituximab will be administered in Cycle 1 at a fixed dose of 375 mg/m², once per week for a total of 4 weeks. The first dose of rituximab will be administered on Cycle 1 Day (-7) followed by the second dose a week later on Day (0).

The first dose of PF-05082566 will be given approximately 24 hours after the second weekly, full dose of rituximab (Cycle 1 Day 1). This allows for the observance of any potential reactions to rituximab treatment prior to the initiation of PF-05082566 dosing. In this study, full dose of rituximab is defined as either the planned dose, or for those patients who develop an infusion reaction, as at least 50% of the planned dose. Continuation with protocol activities as scheduled, following administration of less than the planned rituximab dose, requires confirmation of dose acceptability from the Sponsor.

The proposed schedule and duration of infusion may be reconsidered and amended during the study based on the emerging safety and PK **CCI** data.

Duration of Treatment

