7.1.1. Pregnancy Testing

For female patients of childbearing potential, a serum or urine pregnancy test, with sensitivity of at least 25 mIU/mL, will be performed on 2 occasions prior to starting administration of study treatment: once at the start of screening and once at the baseline visit, immediately before administration of the first dose of study treatment. Following a negative pregnancy test result at screening, appropriate contraception must be commenced and a second negative pregnancy test result will be required at the baseline visit before the patient may receive the investigational product. Pregnancy tests will be repeated at every treatment cycle during the active treatment period, at the end of study treatment, and additionally whenever 1 menstrual cycle is missed or when potential pregnancy is otherwise suspected. Additional pregnancy tests may also be undertaken if requested by institutional review boards (IRBs)/ethics committees (ECs) or if required by local regulations. In the case of a positive confirmed pregnancy, the patient will be withdrawn from administration of investigational product but may remain in the study.

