3.7. Baseline Variables

3.7.1. Study Drug, Study Treatment and Baseline Definitions

In this study, ‘**study drug**’ refers to PF-05082566 or rituximab and ‘**study treatment**’ (or ‘**treatment group**’) refers to one of the following:

- PF-05082566 0.006 mg/kg q4wks;
- PF-05082566 0.03 mg/kg q4wks;
- PF-05082566 0.06 mg/kg q4wks;
- PF-05082566 0.12 mg/kg q4wks;
- PF-05082566 0.18 mg/kg q4wks;
- PF-05082566 0.24 mg/kg q4wks;
- PF-05082566 0.3 mg/kg q4wks;
- PF-05082566 0.6 mg/kg q4wks;
- PF-05082566 1.2 mg/kg q4wks;
- PF-05082566 2.4 mg/kg q4wks;
- PF-05082566 5 mg/kg q4wks;
- PF-05082566 10 mg/kg q4wks;
- PF-05082566 0.03 mg/kg q4wks + rituximab 375 mg/m² q1wk x4;
- PF-05082566 0.06 mg/kg q4wks + rituximab 375 mg/m² q1wk x4;
- PF-05082566 0.12 mg/kg q4wks + rituximab 375 mg/m² q1wk x4;
- PF-05082566 0.18 mg/kg q4wks + rituximab 375 mg/m² q1wk x4;
- PF-05082566 0.24 mg/kg q4wks + rituximab 375 mg/m² q1wk x4;
- PF-05082566 0.3 mg/kg q4wks + rituximab 375 mg/m² q1wk x4;
- PF-05082566 0.6 mg/kg q4wks + rituximab 375 mg/m² q1wk x4;
- PF-05082566 1.2 mg/kg q4wks + rituximab 375 mg/m² q1wk x4;

- PF-05082566 2.4 mg/kg q4wks + rituximab 375 mg/m² q1wk x4;
- PF-05082566 5 mg/kg q4wks + rituximab 375 mg/m² q1wk x4;
- PF-05082566 10 mg/kg q4wks + rituximab 375 mg/m² q1wk x4.

Start and end dates of study treatment:

For single agent PF-05082566:

The date/time of first dose of study treatment is the earliest date/time of non-zero dosing of the study drug.

The date/time of last dose of study treatment is the latest date/time of non-zero dosing of the study drug.

For PF-05082566 + rituximab:

The date/time of first dose of study treatment in a combination arm is the earliest date/time of the first non-zero dose date/time for each of the study drugs.

The date/time of last dose of study treatment in a combination arm is the latest date/time of the last non-zero dose date/time for each of the study drugs.

Definition of baseline:

Definition of baseline for efficacy analyses in randomized cohorts

The last measurement prior to randomization will serve as the baseline measurement for efficacy analyses. If such a value is missing, the last measurement prior to the first dose of study treatment will be used as the baseline measurement except for analyses of tumor assessment data where the baseline assessment would be considered as missing.

Definition of baseline for efficacy [CCI] and for safety analyses

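### Table 5 leaves out the Day -7 pregnancy test for Portion B, although the text requires a test immediately before the first dose of study treatment, which is rituximab on Day -7

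*Protocol*

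**What the plan says.** **The requirement.** Protocol Table 5, footnote 15, covers the expansion cohorts of both portions. Pregnancy testing "will be performed on 2 occasions prior to starting administration of study treatment", namely "once at the start of screening and once at the baseline visit, immediately before administration of the first dose of study treatment". Section 7.1.1 repeats this and adds a condition on the result: "Following a negative pregnancy test result at screening, appropriate contraception must be commenced and a second negative pregnancy test result will be required".

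**What counts as study treatment in Portion B.** Exclusion criterion 3 (Section 4.2) defines the term for the whole protocol: "study treatment includes rituximab in Portion B". Section 5 puts the first rituximab dose on Cycle 1 Day -7 and the second a week later on Day 0, with PF-05082566 following on Day 1. SAP Section 3.7.1 takes the same view: the "first dose of study treatment in a combination arm is the earliest date/time of the first non-zero dose date/time" of either drug.

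**The grid.** The Table 5 row for the pregnancy test is marked at Screening, Day 1, Cycle ≥2 Day 1 and End of Treatment. The columns for Day -7 and Day 0, which exist only for Portion B, are blank. Table 3, the Portion B dose-escalation schedule, carries the same footnote wording and marks Screening, Day -7, Day 0 and Day 1.

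**The concern.** The grid and its footnote give different instructions for the same test. For Portion A they agree, because Day 1 is the first dose. For Portion B, Day 1 comes after two rituximab infusions, so a test marked there cannot be the one that precedes first exposure.

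Sites commonly plan visits from the grid. One that did so here would start rituximab on the screening result alone. That test is done at the start of a window reaching back up to 28 days before enrollment. The protocol itself treats rituximab as a pregnancy risk: Section 4.3 asks women of childbearing potential to continue contraception for 12 months after the last rituximab dose. Most of the exposure still lay ahead at this amendment: Section 3.1.2 plans up to 100 patients with follicular lymphoma, of whom 10 had been enrolled by September 2016.

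**Working it through.** This is mainly a comparison of the grid with the text. The little arithmetic involved is shown.

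**1. When is the first dose of study treatment in Portion B?** Exclusion criterion 3 includes rituximab in study treatment, Section 5 starts rituximab on Day -7, and SAP Section 3.7.1 dates first treatment from the earliest dose of either drug. All three lead to Day -7.

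**2. Pregnancy tests up to and including the first-dose visit.**

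| Source | Tests counted | Number |
|---|---|---|
| Footnote 15 and Section 7.1.1 | start of screening; immediately before first dose | 2 |
| Table 5 grid, Portion A (first dose Day 1) | Screening, Day 1 | 2 |
| Table 5 grid, Portion B (first dose Day -7) | Screening | 1 |
| Table 3 grid, Portion B (first dose Day -7) | Screening, Day -7 | 2 |

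Only the Table 5 grid for Portion B falls short: 2 - 1 = 1 test missing.

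**3. Could the blank come from a shifted column in the extracted text?** The row has a full set of cells. Neighbouring rows agree with their own footnotes: the ECG row is marked at Day -7 and Day 1, as footnote 11 says, and the urinalysis row at Screening, Day 1 and End of Treatment, as footnote 14 says. A shifted column would have broken these matches.

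**4. How late would the retest be under the grid alone?** SAP Section 6.5.3.4 computes the Cycle 1 delay of PF-05082566 in Portion B as study day of first dose minus 9. Planned Day 1 is therefore study day 9, with Day -7 as study day 1.

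- Time from first rituximab to the Day 1 test: 9 - 1 = 8 days.
- Rituximab is planned on Days -7, 0, 7 and 14. Doses before the Day 1 test: Day -7 and Day 0, which is 2 of 4.

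**5. The footnote pointer.** In the machine-read text the Table 5 row is labelled "Pregnancy test ¹⁴". In Table 3 that number leads to the pregnancy footnote. In Table 5, footnote 14 is urinalysis and footnote 15 is the pregnancy test. Superscripts read by machine are not fully reliable, so this is secondary and should be checked against the original.

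**The case against.** The strongest reply is that nothing required is missing from the protocol. Footnote 15 and Section 7.1.1 state the right timing, and a site that reads them will test on Day -7. Other controls also apply:

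- a negative screening test (inclusion criterion 11) and exclusion of pregnant patients (exclusion criterion 13);
- two highly effective contraceptive methods (inclusion criterion 12 and Section 4.3), with contraception in place after the negative screening test;
- a retest whenever a period is missed or pregnancy is suspected.

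Even the grid gives a retest before PF-05082566. All of this stands, and it limits the seriousness of the point. It does not reconcile the grid with the text.

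A second reply is that Section 7.1.1 ties the second negative result to receipt of investigational product, and Section 5 says rituximab has that status in only some countries. Elsewhere, a Day 1 test would satisfy that one sentence. It would still fail the requirement, in the same section and in footnote 15, for a test immediately before the first dose of study treatment.

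A third reply concerns the supporting comparisons. Footnote 12 pairs the two portions' starting visits for hematology and chemistry ("No need to repeat on C1D1 for Portion A or Cycle 1 Day -7 [C1D(-7)] for Portion B"), but urinalysis has no Day -7 mark, so Table 5 follows no uniform rule. Table 3 also marks Day 0, which its own footnote does not require. Both observations are fair. They weaken the analogies, but the conclusion rests on the definition of study treatment and the blank cell.

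**Conclusion.** The inconsistency is real. For Portion B, the Table 5 grid shows one pregnancy test before first dose and the text requires two. A site following the grid alone would give 2 of 4 rituximab doses before retesting, with the retest 8 days after first exposure.

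The conclusion rests on reading study treatment as exclusion criterion 3 and SAP Section 3.7.1 define it, and on the Table 5 row having been extracted correctly, which the neighbouring rows support. The documents do not state how many women of childbearing potential are affected. The point concerns a safety schedule. It does not affect sample size, interval estimates or any planned analysis. It is worth correcting because the grid, as written, contradicts a safeguard that the protocol requires.

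**What to change.** In the Table 5 pregnancy-test row, add a mark at Day -7, for Portion B only and before rituximab. Keep the Day 1 mark for both portions. A Day 0 mark is not needed to meet the footnote. Check the row's superscript in the original document and, if it reads 14, change it to 15. As optional tidying, Section 7.1.1 could refer to study treatment where it now says investigational product, which would remove the country-dependent reading.

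The cost is one mark and, at most, one footnote number. The test is already required by footnote 15, and Day -7 is an existing Portion B visit at which Table 5 already schedules hematology, chemistry and coagulation samples.
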